Follow-Up	(4) Intervention (double-blind, crossover) : Arm 1: Session 1 = rTMS and exercise; Session 2 = sham rTMS and exercise Arm 2: Session 1 = sham rTMS and exercise; Session 2 = rTMS and exercise
Efficacy Evaluations	Quadriceps maximal voluntary isometric contraction (MVIC) Change in Quadriceps Central Activation Ratio (%)
Pharmacokinetic Evaluations	NA
Safety Evaluations	Adverse events will be determined using the NC TraCS Safety Monitoring Plan guidelines for Minimal Risk Studies. The Grading Scale is as follows: Mild - Event results in mild or transient discomfort, not requiring intervention or treatment; does not interfere with daily activities (e.g. transient muscle soreness) Moderate - Event is sufficiently discomforting so as to limit or interfere with daily activities; may require additional interventional treatment (e.g. musculoskeletal injury such as a muscle strain) Severe - Event results in significant symptoms that prevent normal daily activities; may require invasive intervention In the event that two adverse events are classified as either moderate or severe the study will be placed on hold in order to reassess the study procedures in order to decrease the risk of another adverse event.

Statistical And Analytic Plan	
Aim 1: We will compare between limb differences and use correlation analyses to examine associations between measures of neural excitability, pain, pain sensitization, quadriceps function, timed-up-and-go test, and pain catastrophizing.
 
Aim 2: We will use a repeated measures analysis of variance (ANOVA) to compare the pre- and post-intervention outcomes.

DATA AND SAFETY MONITORING PLAN	
In the event that two adverse events are classified as either "moderate" or "severe", based on the NC TraCS Safety Monitoring Plan guidelines, the PI will place the study on hold in order to reassess the study procedures to decrease the risk of another adverse event.
 
Individuals will be withdrawn from the study if they experience any of the following:
 
1) Signs of musculoskeletal injury2) Failure or inability to comply with the study procedures3) Any sign of moderate or severe adverse effects associated with TMS or rTMS.4) Pregnancy

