If the subject reports less than 7 hours of sleep we further explore the sleep pattern. We will ask the participant if this is a normal amount of sleep for him/her and if he/she had a nap in the past 24 hours. If the total reported amount of sleep is off by 2 hours or more compared to their normal pattern, we will consider this a sign of sleep deprivation and the subject will be rescheduled to return for testing on another day.

There is a very rare risk of seizure. TMS stimulates the neurons in the brain at a level below what is required to cause a seizure, although eight seizures have been noted in the literature in the past 20 years. Six of them have been in healthy volunteers (without any history of seizures, brain masses or traumatic brain injuries). The risk of seizure induction is related to the intensity, duration, frequency and rest interval of stimulation. Following the adoption and widespread use of the safety guidelines, 1 seizure has been reported since 1997 and it involved parameters of higher settings than the safe range (Rossi, 2009). The stimulation with the parameters and settings we propose to use are adjusted to the participant's motor threshold and we have included a long "on" to "off" ratio during the repetitive TMS intervention. Our ratio of 1:11 well exceeds the safety guideline of 1:2. To be safe, we have excluded individuals with a history of seizures or epilepsy. We have also excluded people with a history of head injury and medications that could lower the seizure threshold. By following all of the published safety guidelines, the risk of seizure is rare.

There are always possibilities that unknown side effects may occur during or following testing.

Participants will be monitored throughout the study for any adverse events and will be withdrawn from the study if they report any adverse events associated with either the testing or the intervention. In the event that a participant sustains an injury during the study, they will be referred to the appropriate medical personnel on campus (i.e. Campus Health Services or the UNC Hospitals Emergency Room).

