4.7 Subject Completion/ Withdrawal procedures

Participants may withdraw at any time in the study. Participants will be monitored throughout the study for any adverse events and will be withdrawn from the study if they report any adverse events associated with either the testing or the intervention. In the event that a participant sustains an injury during the study, they will be referred to the appropriate medical personnel on campus (i.e. Campus Health Services or the UNC Hospitals Emergency Room). Most women enrolled will not be of childbearing age. If patients are pregnant or plan to be become pregnant during the study we will exclude these patients from the study as these changes may have an effect on the physiology that could alter the response to the rTMS and other measures.

Individuals will be withdrawn from the study if they experience any of the following:

- 1) Signs of musculoskeletal injury
- 2) Failure or inability to comply with the study procedures
- 3) Any sign of moderate or severe adverse effects associated with TMS or rTMS.
- 4) Pregnancy

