6.5 Interim Analysis

No interim analysis is planned for the statistical analyses. For safety, in the event that two adverse events are classified as either "moderate" or "severe", based on the NC TraCS Safety Monitoring Plan guidelines, the study will be placed on hold in order to reassess the study procedures in order to decrease the risk of another adverse event.

7 STUDY INTERVENTION (drug, device or other intervention details)

Repetitive TMS (rTMS) + Exercise Protocol delivered via pulses in a series using the Magstim Rapid2. The frequency of the repetitive pulses is set to 10 Hz, 5 seconds on and 55 seconds off for 15 minutes to deliver a total of 750 pulses. The intensity will be set at 70% of active motor threshold (AMT). During the on time, the subject will perform an isometric exercise for the thigh muscle at 5% of maximum (MVIC). The subject will rest during the off interval to minimize fatigue. The ratio of "on" to "off" stimulus of rTMS well exceeds the recommended safety guidelines for rTMS maximum safe

duration (Wassermann, 1998). These guidelines recommend that the "off" time be at least twice as long as the duration of the "on" time. We are using a 1:11 ratio. The coil will be encased in a black mesh bag with a plastic mesh between the coil and the scalp to mimic the sham condition. This will allow to allow cooling but hide the intervention condition.

For sham rTMS + Exercise the protocol will be the same with the exception that Mu-metal will be placed between the coil and the scalp. The mu-metal serves as a shield for preventing most of the magnetic energy transmission. The coil will be encased in a black mesh bag to allow cooling but hide the mu material. During the "true" rTMS condition, we will also use the mesh bag over the coil to blind the condition.

8 STUDY INTERVENTION ADMINISTRATION (if applicable)

Participants will be randomized into blocks of 3 in an A:B, B:A order, where A is the "true" intervention session and B is the "sham" control session. Half the subjects will be A:B order and half B:A. The randomization list will be created by the biostatistician.

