9 SAFETY MANAGEMENT

The principal investigator, [name], will oversee data collection monitoring and all issues related to participant safety, data collection protocols, and participant confidentiality. [name] will personally collect any adverse event that occurs during the data collection sessions in the Sports Medicine Research Laboratory.

The participant's vital signs will be taken before any active testing, TMS, or rTMS. If the blood pressure or heart rate is low (< 90 systolic, < 60 diastolic, < 50 beats/min), the participant will be advised of the higher risk of syncope and excluded. If the participant reports being light headed or sleep deprived, the data collection session will be stopped and rescheduled.

All researchers involved with TMS and rTMS will be trained on management of syncope and seizures. We will minimize risk of seizure by screening participants for a seizure history and tailoring each person's TMS intensity to their motor (and indirectly seizure) threshold. We will exclude subjects if they are taking medications that are linked to reducing seizure thresholds. We will minimize hearing damage from rTMS by having all participants wear earplugs to protect their hearing during the TMS sessions.

Before maximum voluntary isometric contraction (MVIC) testing participants will be given a warm-up. Participants will also go through a graded warm up to acclimate to the stimulation needed for quadriceps voluntary activation testing. The 5-minute warm-up prior to testing is designed to reduce the risk of muscle soreness and/or injury during testing. The electrical stimulator will always be connected to the stimulus isolation unit to ensure that the subject is isolated from fluctuations in the building's power supply. Additionally, most members of the research team are certified/licensed health

care providers (Licensed Physical Therapist or Certified Athletic Trainer), and all are trained and certified to provide First Aid and CPR. Any safety concerns (i.e. musculoskeletal injury) would likely be recognized immediately during testing and the research team will monitor participants for adverse events during both testing and intervention sessions.

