The research team will refer any individuals who experience adverse events to the Stallings-Evans Sports Medicine Center (located in the building adjacent to Fetzer Hall where the Neuromuscular and Sports Medicine Research Laboratories are located) or Emergency Medical Services depending on the nature and severity of the adverse event issues.

Adverse events will be determined using the NC TraCS Safety Monitoring Plan guidelines for Minimal Risk Studies. The Grading Scale is as follows:

Mild - Event results in mild or transient discomfort, not requiring intervention or treatment; does not interfere with daily activities (e.g. transient muscle soreness)

Moderate - Event is sufficiently discomforting so as to limit or interfere with daily activities; may require additional interventional treatment (e.g. musculoskeletal injury such as a muscle strain)

Severe - Event results in significant symptoms that prevent normal daily activities; may require invasive intervention

In the event that two adverse events are classified as either moderate or severe the study will be placed on hold in order to reassess the study procedures in order to decrease the risk of another adverse event.

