10 DATA COLLECTION AND MANAGEMENT

The principal investigator will oversee data collection monitoring and all issues related to participant safety, data collection protocols, and participant confidentiality. All adverse events will be reviewed and investigated by [name], a licensed physical therapist. Data will be reviewed by two investigators to ensure quality at all stages of reduction, post processing and imputation into statistical software packages. All data will be de-identified and stored in secure password protected computers. The principal investigator will randomly check data reduction, post-processing, and imputation at time points throughout the study. We will utilize the REDCap software to secure data management.

Each subject and his/her associated information will be identified by a subject identification number. Code lists linking the subject identification number and his/her name and email address will be viewed by the research team only, and will be secured in the Neuromuscular Research Laboratory on a password-protected computer. Email addresses will be obtained solely for the purpose of contacting participants to schedule testing. All data will be de-identified and stored in electronic format on both the data collection computer and the principal investigator's personal computer, as well as a number of backup storage devices. Computer access will be protected via confidential passwords, and backup devices will be stored in the Neuromuscular Research Laboratory, which is secured via keycard entry.

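### The only mandatory study hold needs two Moderate or Severe adverse events of any kind, so a single seizure does not by itself require stimulation to pause

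*Combined protocol and SAP*

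**What the plan says.** The hold rule is stated four times: in the Synopsis under Safety Evaluations, in the Synopsis under Data and Safety Monitoring Plan, in Section 6.5, and in Section 9. Section 9 reads: "In the event that two adverse events are classified as either moderate or severe the study will be placed on hold". The Data and Safety Monitoring Plan entry names who acts and why: "the PI will place the study on hold in order to reassess the study procedures to decrease the risk of another adverse event". Section 6.5 gives the same purpose and plans no interim statistical analysis.

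The scale attached to the rule (Synopsis, Safety Evaluations; Section 9) has three grades: Mild, Moderate and Severe. The description of Moderate ends with "may require additional interventional treatment (e.g. musculoskeletal injury such as a muscle strain". Section 5.3 describes risks on a separate scale, which has a fourth, life-threatening grade. Neither scale assigns a grade to seizure.

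Other provisions apply to single events:

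- Section 4.7 withdraws a participant for "Any sign of moderate or severe adverse effects associated with TMS or rTMS". The same section also has a broader sentence that withdraws anyone reporting an adverse event linked to testing or intervention.
- Section 9 says "All researchers involved with TMS and rTMS will be trained on management of syncope and seizures". It also refers affected individuals to the sports medicine center or emergency services.
- In Section 10, "All adverse events will be reviewed and investigated by" a licensed physical therapist.

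On the risk itself, Sections 1.2 and 5.3 call seizure very rare and say that "1 seizure has been reported since 1997 and it involved parameters of higher settings than the safe range".

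**The concern.** The hold exists so that procedures can be reassessed before someone else is harmed. A seizure fits that purpose better than any other event the plan names. The stimulation recipe is common to all participants: 10 Hz, 750 pulses, 70% of active motor threshold. People with seizures or epilepsy, head injury or threshold-lowering medication are screened out. A seizure would therefore mean either that screening missed someone or that the settings were not safe for someone who passed it. Both possibilities bear on the next participant.

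The rule counts events without regard to type. A seizure graded Moderate or Severe is one of the two events needed, the same weight as a strain from strength testing. If it were graded Mild it would not count at all. What is at stake is participant safety between a first seizure and the next stimulation session. The efficacy analysis is not affected.

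**Working it through.** **Step 1. Apply the rule as written.** The threshold of two is stated, not derived, so the plan has no figure to reproduce.

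| Event history | Count toward two | Hold required? |
|---|---|---|
| Two muscle strains, each Moderate | 2 | Yes |
| One seizure, graded Moderate or Severe (my reading) | 1 | No |
| One seizure plus one earlier Moderate event of any kind | 2 | Yes |
| One seizure, graded Mild | 0 | No |

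**Step 2. Look for another provision that would stop stimulation after one seizure.** Withdrawal (Section 4.7) and referral (Section 9) concern the person already affected. Staff training (Section 9) concerns managing the event. Review (Section 10) covers all events, but it has no time limit and is not tied to stopping sessions. No section makes a single seizure, or a single life-threatening event, a trigger for a hold.

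**Step 3. How often would seizures alone reach the count of two?**

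Inputs:
- n = 20 participants (Section 3.3).
- p = chance of a seizure per participant over the whole study. The plan gives no value, so 0.1% and 0.5% are assumptions. The 1% value is the upper limit of the plan's rare category (below 1%, Section 5.3). It serves as a bound, not an estimate.
- Participants are assumed independent.

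Formulas:
- P(at least 1) = 1 − (1 − p)^20
- P(2 or more) = 1 − (1 − p)^20 − 20 × p × (1 − p)^19
- P(exactly 1, given at least 1) = [P(at least 1) − P(2 or more)] / P(at least 1)

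At p = 0.001:
- P(at least 1) = 1 − 0.999^20 = 0.0198
- P(2 or more) = 1 − 0.999^20 − 20 × 0.001 × 0.999^19 = 0.000188
- P(exactly 1, given at least 1) = (0.0198 − 0.000188) / 0.0198 = 0.991

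| Assumed p | At least one seizure | Two or more | Only one, if any |
|---|---|---|---|
| 0.1% | 2.0% | 0.02% | 99% |
| 0.5% | 9.5% | 0.45% | 95% |
| 1% (bound) | 18.2% | 1.7% | 91% |

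If a seizure occurs, it is very probably the only one. A mandatory hold would then depend on a Moderate or Severe event of some other kind.

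**The case against.** The case on the other side has real substance.

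- **Single events are already handled.** The principal investigator oversees all participant-safety matters, events are reviewed, the participant leaves the study, and nothing prevents an earlier pause. Twenty participants with three sessions each make 20 × 3 = 60 sessions over 12 to 16 months, or roughly one a week. Review before the next session is feasible without a written trigger. This stands, and it narrows the gap to the absence of a requirement. It does not close it, because the plan chose to write a mandatory rule and that rule passes over its gravest named TMS risk.
- **The rates are assumed.** The plan calls seizure very rare, excludes many people at risk, and uses a 1:11 on-off ratio. Nothing in it supports 0.5% or 1% as realistic. That few seizures would come in pairs follows from any small p with n = 20. This stands too. The conclusion rests on the wording of the rule, not on a rate.
- **Other requirements may apply.** Events are determined under an external safety-monitoring guideline that is not reproduced, an investigational device exemption was requested, and the study has IRB oversight. Any of these might require a pause. The point is therefore limited to what the protocol and SAP themselves require.

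A reader might infer that the plan ignores a single seizure, or that it obliges staff to carry on stimulating. The documents support neither: they provide for withdrawal, referral and review, and leave a voluntary pause open. A reader might also take 18% as the expected chance of a seizure in this trial. It is only the value at the edge of the plan's rare category.

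**Conclusion.** The concern holds in a limited form. All four statements of the rule require two Moderate or Severe events of any type. A single seizure therefore does not oblige anyone to stop stimulation or reassess procedures before the next participant is treated, whereas two muscle strains do. Existing safeguards protect the affected participant and provide for review, but do not make that review a condition of continuing.

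Seizures alone would reach the count of two with probability about 0.02% at an assumed 0.1% per participant, and below 1.7% anywhere under the plan's 1% ceiling, given 20 independent participants. One seizure in 20 would not disprove a true rate below 1%, so the argument is not that a single event shows the risk was misjudged. It is that this event most clearly calls for the reassessment the rule was written to secure. The point is worth correcting because the remedy is specific and cheap.

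**What to change.** Add one sentence to all four statements of the rule (Synopsis, Safety Evaluations; Synopsis, Data and Safety Monitoring Plan; Section 6.5; Section 9):

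> *Any single seizure, or any other adverse event the principal investigator judges life-threatening, also places the study on hold; no further TMS, rTMS or sham session is run until the event and the study procedures have been reviewed.*

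Keep the count of two for other Moderate or Severe events. For consistency, add a life-threatening grade to the scale used for the hold (Synopsis, Safety Evaluations; Section 9), which now stops at Severe. The Section 5.3 scale already has that grade and needs no change.

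The cost is a short protocol amendment, with no change to endpoints, sample size or analysis. The downside is that one event can pause a 20-person study. Through seizures alone, that chance is about 2% at the assumed 0.1% rate and below 18.2% under the plan's 1% ceiling. Other life-threatening events would add to it, and the plan gives no rate for those.

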10 DATA COLLECTION AND MANAGEMENT

The principal investigator will oversee data collection monitoring and all issues related to participant safety, data collection protocols, and participant confidentiality. All adverse events will be reviewed and investigated by [name], a licensed physical therapist. Data will be reviewed by two investigators to ensure quality at all stages of reduction, post processing and imputation into statistical software packages. All data will be de-identified and stored in secure password protected computers. The principal investigator will randomly check data reduction, post-processing, and imputation at time points throughout the study. We will utilize the REDCap software to secure data management.

Each subject and his/her associated information will be identified by a subject identification number. Code lists linking the subject identification number and his/her name and email address will be viewed by the research team only, and will be secured in the Neuromuscular Research Laboratory on a password-protected computer. Email addresses will be obtained solely for the purpose of contacting participants to schedule testing. All data will be de-identified and stored in electronic format on both the data collection computer and the principal investigator's personal computer, as well as a number of backup storage devices. Computer access will be protected via confidential passwords, and backup devices will be stored in the Neuromuscular Research Laboratory, which is secured via keycard entry.

11 RECRUITMENT STRATEGY

A multi-pronged approach will be utilized to identify study participants. Participants will be recruited through: 1) direct referral from physicians, 2) subjects who have been screened for participation in Dr.

[name]'s research study but were excluded based on their central activation ratio or pain score, and 3) A search of patients with knee osteoarthritis will be conducted using the Carolina Data Warehouse (CDW) or via practice records systems such as EPIC.

Physicians in the Department of Medicine (Divisions of Family Medicine, Orthopaedics, and Rheumatology) at the University of North Carolina at Chapel Hill will provide study flyers to knee OA patients treated in the clinics. [name] and [name], co-investigators on this study, have appointments in Family Medicine and Orthopedics. [name] and [name] will not screen or enroll subjects in the study but will provide flyers to the prospective participants and ask interested patients for permission to share contact information with the study team. Approved study personnel will be in constant contact with physicians and clinic personnel to collect knee OA patient contact information and follow-up with OA patients treated in their clinics who have indicated willingness to be contacted. We will remind participating physicians and clinic administrators about the need for patient referrals with regular email alerts that report accrual rates to date.

We expect the majority of the participants will come from a list of prospective subjects from [name] lab. Subjects with knee osteoarthritis who have been screened by [name] and others in the Neuromuscular Research Laboratory but were excluded from his study (IRB# 15-1150) will be identified. [name] has more stringent inclusion criteria for pain and level of central activation deficits that are not required for this study. Subjects who have participated in research and indicated they would be willing to return for other studies will be contacted by phone or email to invite to participate. In his ongoing study, subjects who are excluded by [name] will be offered a flyer. If interested, the subject will be scheduled to return to the lab for screening and participation in this study.

Secondary recruitment methods will include searching the Carolina Data Warehouse for Health. Study personnel will identify potential patients using knee OA ICD-9/10 codes, and send an authorized recruitment letter to each participant. A recruitment method using EPIC, the healthcare software used at UNC Hospitals that provides past and current medical information, will also be employed. EPIC will also be used to identify potential participants from the broad list of result obtained from the Data Warehouse. Authorized study personnel, who have been EPIC and HIPAA trained will obtain medical record numbers that correspond to OA ICD-9 and 10 codes from Data Warehouse personnel. By reviewing medical records using EPIC, authorized study personnel will determine which participants have X-rays within the past 6-months and a confirmed OA diagnosis. The primary care doctor of prospective participants will be contacted for approval before a letter is sent to the potential subject. Potential participants found in this way will be sent an authorized recruitment letter which will indicate that the patient's primary care doctor was consulted regarding the patient's participation in this research project.

Emails, flyers, and recruitment letters will have the contact information for the study. Those who have indicated an interest in participating in knee arthritis research, either from the physicians' clinics, [name] lab, or responding to these materials will be contacted for screening. Subjects will be contacted by the PI or the study coordinator by telephone or in person in the laboratory or clinic.

